#### Type of Participant and Disease Characteristics:

2. Participants who are willing and able to comply with all scheduled visits, treatment plan, laboratory tests, lifestyle considerations, and other study procedures.
3. Documented histologic or cytologic diagnosis of advanced metastatic NSCLC, advanced/unresectable pancreatic cancer, or metastatic colorectal cancer by American Joint Committee on Cancer (AJCC) criteria
4. Cachexia, defined using Fearon's criteria:
  - Body Mass Index (BMI)  $<20 \text{ kg/m}^2$  with involuntary weight loss of  $>2\%$  within 6 months prior to screening; or
  - Involuntary weight loss of  $>5\%$  within 6 months prior to screening irrespective of BMI; or

If medical record documentation is unavailable, patient's report will suffice to estimate involuntary body weight loss.
5. Serum GDF-15 levels of  $\geq \text{CCI}$  (as measured using the Investigational Use Only Roche Elecsys GDF-15 assay) at screening.

6. Participants considered eligible for systemic anti-cancer treatment/therapy at the time of screening, who:
  - Are diagnosed with advanced metastatic NSCLC who will be treated with:
    - A platinum + pemetrexed  $\pm$  pembrolizumab; or
    - A platinum + nab paclitaxel or paclitaxel  $\pm$  pembrolizumab; or
    - Pembrolizumab alone.
  - Are diagnosed with advanced/unresectable pancreatic cancer who will be treated with:
    - FOLFIRINOX; or
    - Nab-Paclitaxel + Gemcitabine;
    - Gemcitabine.
  - Are diagnosed with metastatic colorectal cancer who will be treated with:
    - FOLFOX +/- Biologic (Bevacizumab or Cetuximab/Panitumumab); or
    - FOLFIRI +/- Biologic (Bevacizumab or Cetuximab/Panitumumab); or
    - FOLFOXIRI +/- Biologic (Bevacizumab or Cetuximab/Panitumumab); or
    - Pembrolizumab for MSI-H.
  - Will be entering the study at the first or second cycle of their current course of anti-cancer treatment/therapy.

Note: Other therapies can be considered upon discussion with the Pfizer medical monitor.

7. Adequate liver function as evidenced by liver enzymes, including:

- Total serum bilirubin  $\leq$ 1.5 x upper limit of normal (ULN) unless the participant has documented Gilbert syndrome;
- Aspartate and Alanine aminotransferase (AST and ALT)  $\leq$ 2.5 x ULN;  $\leq$ 5.0 x ULN if there is liver involvement by the tumor;
- Alkaline phosphatase  $\leq$ 2.5 x ULN ( $\leq$ 5 x ULN in case of bone metastasis).

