## **7. DISCONTINUATION OF STUDY INTERVENTION AND PARTICIPANT DISCONTINUATION/WITHDRAWAL**

### **7.1. Discontinuation of Study Intervention**

In rare instances, it may be necessary for a participant to permanently discontinue investigational product. If investigational product is permanently discontinued, the participant will remain in the study for follow up. Note that discontinuation of investigational product does not represent withdrawal from the study.

If a safety or tolerability concern arises, in particular if not responsive to symptomatic management, dosing with IP may be stopped in an individual participant at investigator discretion.

Any participant who prematurely withdraws after being randomized and during active study intervention, (Day 1 through Week 12) should return for an early withdrawal visit and then enter into the follow-up period.

See [Section 1.3](#) for data to be collected at the time of intervention discontinuation and follow-up and for any further evaluations that need to be completed.

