#### **7.1.1. Criteria for Discontinuation**

Discontinuation of IP must occur for a participant meeting any of the following conditions:

- Criteria for a potential Hy's law case are met (see [Appendix 6](#)).
- Intent to become pregnant or pregnancy confirmed by serum beta human chorionic gonadotropin ( $\beta$ -hCG) testing.

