**Table 3. Protocol-Required Safety Laboratory Assessments**

Hematology	Chemistry	Urinalysis	Other
Hemoglobin	BUN/urea and Creatinine a	pH	Pregnancy test (<math>\beta</math>-hCG)c
Hematocrit	Glucose	Glucose (qual)	At screening only:
RBC count	Calcium	Protein (qual)	FSH d
MCV	Sodium	Blood (qual)	Hepatitis B surface antigen
MCH	Potassium	Ketones	Hepatitis C antibody
MCHC	Chloride	Nitrites	HIV
Platelet count	Total CO 2 (bicarbonate)	Leukocyte esterase	
WBC count	AST, ALT	Urobilinogen	
Total neutrophils (Abs)	Total bilirubin	Urine bilirubin	
Eosinophils (Abs)	Alkaline phosphatase	Microscopy b	
Monocytes (Abs)	Uric acid		
Basophils (Abs)	CRP		
Lymphocytes (Abs)	Pre-albumin		
	Albumin		
	Total protein		

Abbreviations: Abs = absolute; ALT = alanine aminotransferase; AST = aspartate aminotransferase;  $\beta$ -hCG = beta-human chorionic gonadotropin; BUN = blood urea nitrogen; CO2 = carbon dioxide; CRP = C-reactive protein; FSH = follicle-stimulating hormone; MCH = mean corpuscular hemoglobin; MCHC = mean corpuscular hemoglobin concentration; MCV = mean corpuscular volume; MDRD = Modification of diet in renal disease; pH = power of hydrogen; qual = qualitative; RBC = red blood cell; WBC = white blood cell.

a. Glomerular Filtration Rate (GFR) will be calculated using the modification of diet in renal disease (MDRD) equation.

b. Only if urine dipstick is positive for blood, protein, nitrites, or leukocyte esterase.

c. Local urine testing will be standard for the protocol unless serum testing is required by local regulation or institutional review board/ethics committee (IRB/EC). Serum or urine  $\beta$ -hCG for female participants of childbearing potential.

d. For confirmation of postmenopausal status only.

Investigators must document their review of each laboratory safety report.

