## 10.6. Appendix 6: Liver Safety: Suggested Actions and Follow-up Assessments

### Potential Cases of Drug-Induced Liver Injury

Humans exposed to a drug who show no sign of liver injury (as determined by elevations in transaminases) are termed “tolerators,” while those who show transient liver injury, but adapt are termed “adaptors.” In some participants, transaminase elevations are a harbinger of a more serious potential outcome. These participants fail to adapt and therefore are “susceptible” to progressive and serious liver injury, commonly referred to as drug-induced liver injury (DILI). Participants who experience a transaminase elevation above 3 times the upper limit of normal ( $\times$  ULN) should be monitored more frequently to determine if they are an “adaptor” or are “susceptible.”

In the majority of DILI cases, elevations in aspartate aminotransferase (AST) and/or alanine aminotransferase (ALT) precede total bilirubin (TBili) elevations ( $>2 \times$  ULN) by several days or weeks. The increase in TBili typically occurs while AST/ALT is/are still elevated above  $3 \times$  ULN (ie, AST/ALT and TBili values will be elevated within the same laboratory sample). In rare instances, by the time TBili elevations are detected, AST/ALT values might have decreased. This occurrence is still regarded as a potential DILI. Therefore, abnormal elevations in either AST OR ALT in addition to TBili that meet the criteria outlined below are considered potential DILI (assessed per Hy’s law criteria) cases and should always be considered important medical events, even before all other possible causes of liver injury have been excluded.

The threshold of laboratory abnormalities for a potential DILI case depends on the participant’s individual baseline values and underlying conditions. Participants who present with the following laboratory abnormalities should be evaluated further as potential DILI (Hy’s law) cases to definitively determine the etiology of the abnormal laboratory values:

- Participants with AST/ALT and TBili baseline values within the normal range who subsequently present with AST OR ALT values  $>3 \times$  ULN AND a TBili value  $>2 \times$  ULN with no evidence of hemolysis and an alkaline phosphatase value  $<2 \times$  ULN or not available.

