- For participants with baseline AST **OR** ALT **OR** TBili values above the ULN, the following threshold values are used in the definition mentioned above, as needed, depending on which values are above the ULN at baseline:
  - Preexisting AST or ALT baseline values above the normal range: AST or ALT values  $>2$  times the baseline values AND  $>3 \times$  ULN; or  $>8 \times$  ULN (whichever is smaller).
  - Preexisting values of TBili above the normal range: TBili level increased from baseline value by an amount of at least  $1 \times$  ULN **or** if the value reaches  $>3 \times$  ULN (whichever is smaller).

Rises in AST/ALT and TBili separated by more than a few weeks should be assessed individually based on clinical judgment; any case where uncertainty remains as to whether it represents a potential Hy's law case should be reviewed with the sponsor.

The participant should return to the investigator site and be evaluated as soon as possible, preferably within 48 hours from awareness of the abnormal results. This evaluation should include laboratory tests, detailed history, and physical assessment. The possibility of hepatic neoplasia (primary or secondary) should be considered.

In addition to repeating measurements of AST and ALT and TBili for suspected cases of Hy's law, additional laboratory tests should include albumin, creatine kinase (CK), direct and indirect bilirubin, gamma-glutamyl transferase (GGT), prothrombin time (PT)/international normalized ratio (INR), total bile acids, and alkaline phosphatase. Consideration should also be given to drawing a separate tube of clotted blood and an anticoagulated tube of blood for further testing, as needed, for further contemporaneous analyses at the time of the recognized initial abnormalities to determine etiology. A detailed history, including relevant information, such as review of ethanol, acetaminophen (either by itself or as a coformulated product in prescription or over-the-counter medications), recreational drug, supplement (herbal) use and consumption, family history, sexual history, travel history, history of contact with a jaundiced person, surgery, blood transfusion, history of liver or allergic disease, and potential occupational exposure to chemicals, should be collected. Further testing for acute hepatitis A, B, C, D, and E infection and liver imaging (eg, biliary tract) and collection of serum sample for acetaminophen drug and/or protein adduct levels may be warranted.

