All cases demonstrated on repeat testing as meeting the laboratory criteria of AST/ALT and TBili elevation defined above should be considered potential DILI (Hy's law) cases if no other reason for the liver function test (LFT) abnormalities has yet been found. **Such potential DILI (Hy's law) cases are to be reported as SAEs, irrespective of availability of all the results of the investigations performed to determine etiology of the LFT abnormalities.**

A potential DILI (Hy's law) case becomes a confirmed case only after all results of reasonable investigations have been received and have excluded an alternative etiology.

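### The mandatory Hy's law stop is at best ambiguous, and on its plain reading switched off, for eligible participants who enter with alkaline phosphatase at or above 2 x ULN

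*Protocol*

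**What the plan says.** Protocol Section 7.1.1 lists the conditions under which investigational product has to be stopped: "Discontinuation of IP must occur for a participant meeting any of the following conditions". There are two, a potential Hy's law case and pregnancy (confirmed or intended). The first is defined only by reference to Appendix 6.

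For participants with normal baseline AST/ALT and bilirubin (TBili), Appendix 6 asks for AST or ALT above 3 x ULN and TBili above 2 x ULN, "with no evidence of hemolysis and an alkaline phosphatase value" that is below 2 x ULN or not available.

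If AST, ALT or TBili is above ULN at baseline, then "the following threshold values are used in the definition mentioned above, as needed, depending on which values are above the ULN at baseline". Two substitutions follow, one for AST/ALT and one headed "Preexisting values of TBili above the normal range". There is none for ALP.

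Inclusion criterion 7 (Section 5.1) allows ALP up to 2.5 x ULN, relaxed to "5 x ULN in case of bone metastasis".

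Appendix 6 later returns to the classification: "All cases demonstrated on repeat testing as meeting the laboratory criteria of AST/ALT and TBili elevation defined above" are to be treated as potential cases if no other reason has been found, and reported as SAEs. That sentence does not name ALP.

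**The concern.** The entry criteria and the stopping criteria do not fit together. The protocol knowingly admits participants whose ALP already breaches a condition of its only mandatory liver stop. Appendix 6 accepts that thresholds should depend on baseline values, and it adjusts AST/ALT and TBili accordingly, but not ALP. For the bone-metastasis allowance, the protocol itself links the raised ALP to bone, so the value says little about the pattern of a later liver injury.

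What is at stake is the mandatory element. Two participants with the same AST/ALT and TBili would be treated differently, one required to stop and the other left to discretion, because of an ALP value that was present and accepted at entry. The automatic SAE label for potential Hy's law cases becomes uncertain in the same way. The trial is the first use of this antibody in patients with cancer and cachexia, and it has no data monitoring committee (Protocol Sections 4.2 and 9.5.1).

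**Working it through.** The plan gives no figure to reproduce, so the check sets the rules side by side and evaluates them.

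**Inputs** (multiples of ULN)
- ALP at entry: at most 2.5, or at most 5 with bone metastasis (Section 5.1, criterion 7).
- ALP condition for the stop: below 2, or not available (Appendix 6, imported by Section 7.1.1).
- AST/ALT condition: above 3 if normal at baseline. Otherwise above 2 times baseline and above 3, or above 8, whichever is smaller (Appendix 6).
- TBili condition: above 2 if normal at baseline. Otherwise up by at least 1, or above 3, whichever is smaller (Appendix 6).
- ALP is in the chemistry column of Table 3, "Protocol-Required Safety Laboratory Assessments", and safety labs are drawn at every clinic visit in the Schedule of Activities. The not-available route will therefore rarely apply.

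**Step 1: the rule.** Stop = (AST/ALT condition) and (TBili condition) and (ALP below 2 or not available), with no hemolysis taken as met.

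**Step 2: overlap with eligibility.** ALP values from 2 to 2.5, or from 2 to 5 with bone metastasis, are eligible and fail the ALP condition on Day 1.

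**Step 3: evaluate the rule.** Case A has AST/ALT 10 and TBili 5, both normal at baseline. Case B has AST/ALT 21 from a baseline of 5 and TBili 5 from a baseline of 1.5, so both existing adjustments apply.

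| ALP (entry and on treatment) | Case A, current rule | Case B, current rule | Case A, limit of 2 x baseline for entry ALP of 2 or more |
|---|---|---|---|
| 1.0 | stop | stop | stop |
| 1.9 | stop | stop | stop |
| 2.0 | no stop | no stop | stop |
| 2.5 | no stop | no stop | stop |
| 5.0 | no stop | no stop | stop |

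With ALP not available, Case A gives a stop. Case B shows that the existing baseline adjustments do not rescue the rule.

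**Step 4: how far ALP must fall.** From an entry value of b x ULN, ALP has to fall by more than 1 − 2/b before the stop can operate:
- b = 2.5: 1 − 2/2.5 = 20%
- b = 3: 1 − 2/3 = 33%
- b = 4: 1 − 2/4 = 50%
- b = 5: 1 − 2/5 = 60%

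**Step 5: the looser reading.** If the repeat-testing sentence is taken alone, ALP is irrelevant and every row would be a potential case, provided no other cause had been found. That sentence, however, points back to criteria defined earlier in the appendix, and it neither removes nor adjusts the ALP condition. The two readings give opposite answers in the last three rows.

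**Step 6: exposure at issue.** Cohort 1 has 5 planned doses (Section 4.1), so a stop after the first can prevent at most 5 − 1 = 4.

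**The case against.** The strongest objection is that the ALP condition has a purpose: it screens out patterns that are not hepatocellular. Only the 5 x ULN allowance is tied to bone. At 2.0 to 2.5 x ULN without bone metastasis, the protocol gives no bone explanation, and the population includes pancreatic cancer and tumor involvement of the liver. There the condition may be working as intended. This stands in part: the case for a change is weaker in that group. But a fixed limit cannot tell an ALP value accepted at entry from a new rise, whereas a limit relative to baseline can.

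The second objection is that other protections exist. Section 7.1 says that "dosing with IP may be stopped in an individual participant at investigator discretion" if a safety or tolerability concern arises. Section 8 calls for immediate safety concerns to be discussed with the sponsor, and Section 8.2 provides monthly data review. Appendix 6 asks for closer monitoring once transaminases exceed 3 x ULN and sends uncertain Hy's law cases to the sponsor; that last clause follows one about rises separated in time but refers to any such case. All of this stands, and it lowers the practical risk. None of it is a mandatory stop.

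A reader might go further and infer that these participants are unprotected, or that the primary endpoint is compromised. The documents do not support either. Clinically significant laboratory changes are still recorded as AEs (Section 8.2.5, Appendix 3) and graded by CTCAE, and an event can still be an SAE on medical judgment. At most the automatic SAE label is in doubt. A reader might also want a probability that the gap matters. The documents give no share of participants with entry ALP at or above 2 x ULN and no liver-injury rate, so any such figure would rest on assumption alone.

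**Conclusion.** The concern holds as a limited gap in a safety rule, worth correcting but not serious. On the plain reading of Appendix 6, the mandatory liver stop cannot operate for a participant who enters with ALP at or above 2 x ULN for as long as ALP stays there. On the looser reading it can. A mandatory rule should not depend on which sentence the site follows.

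The size is known only as a range of values: 2 to 2.5 x ULN in general, and 2 to 5 x ULN with bone metastasis. The number of participants in that range is unknown, in cohorts of about 8. The conclusion assumes that ALP is measured as scheduled, that hemolysis is absent, and that ALP has not fallen below 2 x ULN by the time of the event. No analysis population or PK summary is affected.

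**What to change.** Add one bullet to Appendix 6, at the same level as the two existing baseline bullets: *For participants with baseline alkaline phosphatase at or above 2 x ULN, whether or not baseline AST, ALT or TBili is raised, the alkaline phosphatase limit in the definition is replaced by less than 2 times the baseline value.* Keep the not-available alternative. Keep the limit of 2 x ULN for everyone whose baseline ALP is below that value, since they have no gap at entry.

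The bullet must stand alone. The present adjustment list opens only for participants with AST, ALT or TBili above ULN at baseline, so a bullet nested there would miss someone whose ALP alone is raised, which is the typical bone-metastasis case.

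The new limit is at least 2 x 2 = 4 x ULN, so it never cancels a stop that the current rule would require. Section 7.1.1 and the SAP need no change.

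The cost is a protocol amendment; ALP is already collected at screening, Day 1 and each later clinic visit. The downside is a few extra stops when liver tests rise for tumor-related or cholestatic reasons, chiefly in participants whose raised entry ALP is not due to bone metastasis. The limit is also generous at the top of the range: entry at 5 x ULN gives 2 x 5 = 10 x ULN. Participants who stop remain in follow-up under Section 7.1, so their later safety data are still collected.

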### **7.2. Participant Discontinuation/Withdrawal from the Study**

A participant may withdraw from the study at any time at his/her own request. Reasons for discontinuation from the study include the following:

- Refused further follow-up;
- Lost to follow-up;
- Death;
- Study terminated by sponsor.

At the time of discontinuing from the study, if possible, an early discontinuation visit should be conducted. See the [SoA](#) for assessments to be collected at the time of study discontinuation and follow-up and for any further evaluations that need to be completed.

If a participant withdraws from the study, he/she may request destruction of any remaining samples taken and not tested, and the investigator must document any such requests in the site study records and notify the sponsor accordingly.

If the participant withdraws from the study and also withdraws consent (see [Section 7.2](#)) for disclosure of future information, no further evaluations should be performed and no additional data should be collected. The sponsor may retain and continue to use any data collected before such withdrawal of consent.

Lack of completion of all or any of the withdrawal/early termination procedures will not be viewed as protocol deviations so long as the participant's safety was preserved.

### **Withdrawal of Consent:**

Participants who request to discontinue receipt of study treatment will remain in the study and must continue to be followed for protocol-specified follow-up procedures. The only exception to this is when a participant specifically withdraws consent for any further contact with him or her or persons previously authorized by the participant to provide this information. Participants should notify the investigator in writing of the decision to withdraw consent from future follow-up, whenever possible. The withdrawal of consent should be explained in detail in the medical records by the investigator, as to whether the withdrawal is only from further receipt of investigational product or also from study procedures and/or posttreatment study follow-up, and entered on the appropriate CRF page. In the event that vital status (whether the participant is alive or dead) is being measured, publicly available information should be used to determine vital status only as appropriately directed in accordance with local law.

### **7.3. Lost to Follow-up**

A participant will be considered lost to follow-up if he or she repeatedly fails to return for scheduled visits and is unable to be contacted by the study site.

The following actions must be taken if a participant fails to return to the clinic for a required study visit:

- The site must attempt to contact the participant and reschedule the missed visit as soon as possible and counsel the participant on the importance of maintaining the assigned visit schedule and ascertain whether or not the participant wishes to and/or should continue in the study;

- Before a participant is deemed lost to follow-up, the investigator or designee must make every effort to regain contact with the participant (where possible, 3 telephone calls and, if necessary, a certified letter to the participant's last known mailing address or local equivalent methods). These contact attempts should be documented in the participant's medical record;
- Should the participant continue to be unreachable, he/she will be considered to have withdrawn from the study.

Discontinuation of specific sites or of the study as a whole is handled as part of [Appendix 1](#).

## **8. STUDY ASSESSMENTS AND PROCEDURES**

The investigator (or an appropriate delegate at the investigator site) must obtain a signed and dated ICD before performing any study-specific procedures.

Study procedures and their timing are summarized in the [SoA](#). Refer to [Appendix 19](#) for a proposed chronology of procedures. Protocol waivers or exemptions are not allowed.

Immediate safety concerns should be discussed with the sponsor immediately upon occurrence or awareness to determine if the participant should continue or discontinue study intervention.

Adherence to the study design requirements, including those specified in the [SoA](#), is essential and required for study conduct.

All screening evaluations must be completed and reviewed to confirm that potential participants meet all eligibility criteria. The investigator will maintain a screening log to record details of all participants screened and to confirm eligibility or record reasons for screening failure, as applicable.

Every effort should be made to ensure that protocol-required tests and procedures are completed as described. However, it is anticipated that from time to time there may be circumstances outside the control of the investigator that may make it unfeasible to perform the test. In these cases, the investigator must take all steps necessary to ensure the safety and well-being of the participant. When a protocol-required test cannot be performed, the investigator will document the reason for the missed test and any corrective and preventive actions that he or she has taken to ensure that required processes are adhered to as soon as possible. The study team must be informed of these incidents in a timely manner.

Any changes in the timing or addition of time points (eg, additional follow up visits) for any planned study assessments must be documented and approved by the relevant study team member and then archived in the sponsor and site study files, but will not constitute a protocol amendment. The IRB/EC will be informed of any safety issues that require alteration of the safety monitoring scheme or amendment of the ICD.

For samples being collected and shipped, detailed collection, processing, storage, and shipment instructions and contact information will be provided to the investigator site prior to initiation of the study.

The total blood sampling volume for individual participants in this study is approximately 490 mL. The actual collection times of blood sampling may change. Additional blood samples may be taken for safety assessments at times specified by Pfizer, provided the total volume taken during the study does not exceed 550 mL during any period of 60 consecutive days.

